# 16.4 Appendix 4: Calculation of Pulmonary Vascular Resistance (PVR)

$$PVR = \frac{mPAP (mmHg) - PCWP(mmHg)}{CO \left(\frac{L}{\min | ||}\right)} \times 80$$

PVR = Pulmonary Vascular Resistance

mPAP = Mean Pulmonary Arterial Pressure

PCWP = Pulmonary Capillary Wedge Pressure

CO = Cardiac Output

TAPSE Tricuspid Annular Plane Systolic Excursion

TASV Tricuspid Annular Systolic Velocity

TFLs Tables, Figures, Listings
TTCW Time to Clinical Worsening
WHO World Health Organization
PAH Pulmonary Arterial Hypertension

SAP Statistical Analysis Plan 6MWD Six Minute Walk Distance 6MWT Six Minute Walk Test

1 Introduction

The Reporting and Analysis documents contain detailed information to aid the production of Statistics & Programming input into the Clinical Study Report (CSR) for trial "CLTP001A12201".

This Statistical Analysis Plan (SAP) has been developed in accordance with Clinical Trial Protocol CLTP001A12201 (Amended Protocol Version 02, released on 01-Mar-2022), and describes the implementation of the statistical analysis planned in the protocol.

1.1 Study design

This is a randomized, participant- and investigator-blinded, placebo-controlled, parallel group study of LTP001 or placebo on top of standard of care in participants with PAH.

Standard of care includes one or more of the following treatments: prostacyclin analogues or receptor agonists (if I.V., dose adjustments must be within 20% of initial stable dose), endothelin receptor antagonists, phosphodiesterase type 5 inhibitors, and soluble guanylate cyclase stimulators.

The study design is described in Figure 1-1. A screening period of 8 weeks will be used to access eligibility prior to randomization. Approximately 44 eligible participants with PAH will be randomized in a 3:1 ratio to either oral LTP001 or placebo daily for 24 weeks in order to achieve 40 patients who complete the treatment period.

An unblinded interim analysis is planned for when approximately 20 participants complete the 24-week treatment period, and may include analyses to assess sample size, efficacy, PK, PD, or safety.

Participants may be allowed to roll over from this study to enter the open label extension study upon approval from health authorities and review boards.

1.2 Study objectives, endpoints and estimands

[figure not shown]
Ok	ojective(s)	Endpoint(s)		
Primary objective(s)		Endpoint(s) for primary objective(s)		
•	To assess the efficacy of LTP001 in participants with pulmonary arterial hypertension (PAH).	Change from baseline right heart catheterization PVR at Week 25		
Secondary objective(s)		Endpoint(s) for secondary objective(s)		
•	To evaluate the effect of LTP001 on Six Minute Walk Distance (6MWD)	Change from baseline in 6MWD at Weeks 13 and 25		
•	To evaluate the effect of LTP001 on hemodynamic parameters other than PVR	 Right heart catheterization assessments including RV pressures, pulmonary artery pressures, wedge pressure, and cardiac output at Week 25 		
•	To assess the effect of LTP001 on measurements of right ventricular function	 Change from baseline in tricuspid annular plane systolic excursion (TAPSE) by echocardiography at Weeks 5, 13, and 25 		
		Change from baseline in tricuspid annular systolic velocity (TASV) by echocardiography at Weeks 5, 13, and 25 Change from baseline of peak velocity of excursion (RV S') by echocardiography at Weeks 5, 13, and 25		
		Change from baseline in fractional area change (FAC) by echocardiography at Weeks 5, 13, and 25		

Objective(s)

- To assess the impact of LTP001 on patient reported outcomes (PRO)
- To assess the safety and tolerability of LTP001
- To assess the impact of LTP001 on Time to Clinical Worsening (TTCW).

Endpoint(s)

- Change from baseline in EmPHasis-10 and PAH-SYMPACT at Weeks 13 and 25
- AEs, SAEs, vital signs, ECGs, safety laboratory measurements
- Time to any of the following:
 - Death
 - Hospital stay (≥ 24 h) due to worsening of PAH.
 Worsening of PAH is defined by the following right heart
 failure related signs and symptoms: syncope or near
 syncope, cyanosis, increase of breathlessness, clinically
 relevant deterioration of exercise capacity, decrease of
 oxygen saturation, increased peripheral edema,
 hepatomegaly, and ascites
 - Worsening of PAH resulting in need for lung transplantation or balloon atrial septostomy
 - Initiation of parenteral prostanoid therapy, chronic oxygen therapy, or any other PAH-specific therapies or need for increase of diuretics for more than 4 weeks due to worsening of PAH
 - Disease progression (switch in modified New York Heart Association/WHO FC by at least one grade).
 - Significant drop in 6MWD (15% from baseline or more) due to PAH-worsening
- Cmax and tmax (Day 1 and Week 25)
- N-terminal fragment of the prohormone B-type natriuetic peptide
- To investigate the pharmacokinetics (PK) of LTP001
- To assess the impact of LTP001 on the N-terminal fragment of the prohormone B-type natriuetic peptide (NT-proBNP)

1.2.1 Primary estimand(s)

Not applicable.

2 Statistical methods

2.1 Data analysis general information

2.1.1 General definitions

Investigational treatment will be LTP001 or placebo.

Date of first administration of study treatment (Day 1) will be defined as the date of the first actual administration of LTP001 or placebo.

Date of last administration of study treatment will be defined as the date of the last actual administration of LTP001 or placebo.

Baseline will be defined as the Day 1 assessment. If this datum is not available, the last predosing assessment will be considered.

Study day will be defined as the number of days since the date of first dose of study treatment (LTP001 or placebo). The date of first dose of study treatment will be defined as Day 1 and the day prior to first dose of will be defined as Day -1.

Therefore, for a particular date, study day will be calculated as follows:

for dates on or after the date of first dose of study treatment,

Study day = Assessment date - Date of first dose administration + 1

The on-treatment period lasts from the date of first administration of study treatment to the End of Study (EOS) visit or the date of last randomized dose if EOS visit is not available. The EOS visit is a follow-up visit that is approximately 30 days after the date of the last actual administration of investigational treatment. For participants who will be enrolled into the open label extension (OLE) study, their EOS visits will be skipped.

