# 9 Discontinuation and completion

# 9.1 Discontinuation from study treatment and from study

# 9.1.1 Discontinuation from study treatment

Discontinuation of study treatment for a participant occurs when study treatment is permanently stopped for any reason (prior to the planned completion of study drug administration, if any) and can be initiated by either the participant or the investigator.

The investigator must discontinue study treatment for a given participant if, he/she believes that continuation would negatively impact the participant's well-being.

Discontinuation from study treatment is required under the following circumstances:

- Participant decision
- Pregnancy
- Any situation in which continued study participation might result in a safety risk to the participant
- Deterioration of PAH requiring hospitalization
- Development of heart failure symptoms consistent with pulmonary hypertension WHO Functional Class IV (symptoms at rest; severe symptoms at exercise)
- Lung transplantation required
- Atrial septostomy required
- Additional PAH directed therapy required beyond the scope of allowed concomitant medication Section 6.2.1) due to disease progression
- Adverse event that is graded severe by the investigator and considered study drug related
- If a liver or renal event occurs, follow guidelines outlined in Section 16.2 (Appendix 2) and Section 16.3 (Appendix 3) regarding discontinuation of study treatment.

If discontinuation from study treatment occurs, the investigator should make a reasonable effort to understand the primary reason for the participant's discontinuation from study treatment and record this information.

Participants who discontinue from study treatment agree to return for the end of treatment and follow-up visits indicated in the Assessment Schedule (refer to Section 8).

If the participant cannot or is unwilling to attend any visit(s), the site staff should maintain regular telephone contact with the participant, or with a person pre-designated by the participant. This telephone contact should preferably be done according to the study visit schedule.

After discontinuation from study treatment, at a minimum, in abbreviated visits, the following data should be collected at clinic visits or via telephone/email contact:

- New / concomitant treatments
- Adverse Events / Serious Adverse Events

The investigator must also contact the IRT to register the participant's discontinuation from study treatment.

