- Drug interrupted/permanently discontinued
- 6. Its outcome

Conditions that were already present at the time of informed consent should be recorded in medical history of the participant.

Adverse events (including lab abnormalities that constitute AEs) should be described using a diagnosis whenever possible, rather than individual underlying signs and symptoms.

Adverse event monitoring should be continued for at least 30 days following the last dose of study treatment.

Once an adverse event is detected, it must be followed until its resolution or until it is judged to be permanent (e.g. continuing at the end of the study), and assessment must be made at each visit (or more frequently, if necessary) of any changes in severity, the suspected relationship to the interventions required to treat it, and the outcome.

Information about adverse drug reactions for the investigational drug can be found in the Investigator's Brochure (IB).

Abnormal laboratory values or test results constitute adverse events only if they fulfill at least one of the following criteria:

- they induce clinical signs or symptoms
- they are considered clinically significant
- they require therapy

Clinically significant abnormal laboratory values or test results must be identified through a review of values outside of normal ranges/clinically notable ranges, significant changes from baseline or the previous visit, or values which are considered to be non-typical in participant with the underlying disease.

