### 10.1.3 SAE reporting

To ensure participant safety, every SAE, regardless of causality, occurring after the participant has provided informed consent and until 30 days following the last administration of study treatment must be reported to Novartis safety immediately, without undue delay, under no circumstances later than within 24 hours of learning of its occurrence. Detailed instructions regarding the submission process and requirements are to be found in the investigator folder provided to each site. Information about all SAEs is collected and recorded on the Serious Adverse Event Report Form; all applicable sections of the form must be completed in order to provide a clinically thorough report.

- 1. SAEs occurring after the participant has provided informed consent until the time the participant is deemed a Screen Failure must be reported to Novartis.
- 2. Randomized OR Treated Participants: SAEs collected between time participant signs ICF until 30 days after the participant has discontinued from study treatment.

All follow-up information for the SAE including information on complications, progression of the initial SAE and recurrent episodes must be reported as follow-up to the original episode immediately, without undue delay, and under no circumstances later than 24 hours of the investigator receiving the follow-up information. An SAE occurring at a different time interval or otherwise considered completely unrelated to a previously reported one must be reported separately as a new event.

If the SAE is not previously documented in the Investigator's Brochure or Package Insert (new occurrence) and is thought to be related to the study treatment, a CMO & PS Department associate may urgently require further information from the investigator for health authority reporting. Novartis may need to issue an Investigator Notification (IN) to inform all investigators involved in any study with the same study treatment that this SAE has been reported.

Suspected Unexpected Serious Adverse Reactions (SUSARs) will be collected and reported to the competent authorities and relevant ethics committees in accordance with EU Guidance 2011/C 172/01 or as per national regulatory requirements in participating countries.

Any SAEs experienced after the 30 day period should only be reported to Novartis Safety if the investigator suspects a causal relationship to study treatment, unless otherwise specified by local law/regulations.

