### 12.5.2 Safety endpoints

For all safety analyses, the safety set will be used. All listings will be presented by treatment group and tables will be presented by treatment group and overall.

Safety summaries (tables, figures) include only data from the on-treatment period with the exception of baseline data which will also be summarized where appropriate (e.g. change from baseline summaries). In addition, a separate summary for death including on treatment and post treatment deaths will be provided. In particular, summary tables for adverse events (AEs) will summarize only on-treatment events, with a start date during the on-treatment period (treatment-emergent AEs).

The on-treatment period lasts from the date of first administration of study treatment to the EOS visit (about 30 days after the date of the last actual administration of any study treatment).

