2.7 Safety analyses

For all safety analyses, the safety set will be used. All listings will be presented by treatment group, and tables will be presented by treatment group and overall. Safety summaries (tables, figures) include only data from the on-treatment period except for baseline data which will also be summarized where appropriate (e.g. change from baseline summaries).

The on-treatment period lasts from the date of first administration of study treatment to the EOS visit (about 30 days after the date of the last actual administration of any study treatment).

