2.7.1 Adverse events (AEs)

All adverse events summarized will be displayed by treatment group and overall. All adverse events listing will be presented by treatment group and participant.

The number (and percentage) of participants with treatment emergent adverse events (events started after the first dose of study medication or events present prior to start of double-blind treatment but increased in severity based on preferred term) will be summarized in the following ways. The definition of the on treatment period is defined in Section 2.1.1.

by treatment, primary system organ class and preferred term.

- by treatment, primary system organ class, preferred term and maximum severity.
- by treatment, Standardized MedDRA Query (SMQ) and preferred term.

Separate summaries will be provided for study medication related adverse events, death, serious adverse events, other significant adverse events leading to discontinuation. In case of sparse events in any of these categories occur, only a listing will be provided if deemed adequate.

A participant with multiple adverse events within a primary system organ class is only counted once towards the total of the primary system organ class.

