2.7.1.1 Adverse events of special interest / grouping of AEs

Not applicable.

2.7.2 **Deaths**

The number and percentage of deaths, including on-treatment and post-treatment deaths, will be summarized by treatment group.

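### SAP 2.1.1 ends the on-treatment period at the last dose for anyone without an EOS visit, so for participants who do not roll over, later AEs and SAEs leave the summary tables although they are collected for 30 days

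*SAP*

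**What the plan says.** SAP 2.1.1 starts the on-treatment period at first dose and ends it at the EOS visit, "or the date of last randomized dose if EOS visit is not available". It places EOS about 30 days after the last dose. It then adds, as a separate statement, that participants entering the open-label extension will skip EOS.

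SAP 2.7 limits safety tables and figures to on-treatment data, apart from baseline. It restates the period with no fallback: "The on-treatment period lasts from the date of first administration of study treatment to the EOS visit". SAP 2.7.1, on the AE tables, says: "The definition of the on treatment period is defined in Section 2.1.1".

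Protocol 12.5.2 has the same restriction ("summary tables for adverse events (AEs) will summarize only on-treatment events, with a start date during the on-treatment period") and also ends the period at EOS, about 30 days after the last dose, again with no fallback.

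On collection, Protocol 10.1.1 states: "Adverse event monitoring should be continued for at least 30 days following the last dose of study treatment". Protocol 10.1.3 requires reporting of "every SAE, regardless of causality, occurring after the participant has provided informed consent and until 30 days following the last administration of study treatment". For people who stop treatment, Protocol 9.1.1 adds: "If the participant cannot or is unwilling to attend any visit(s), the site staff should maintain regular telephone contact with the participant". AEs and SAEs are on its minimum list of data to collect at visits or by telephone or email.

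SAP section 4 declares no change from the protocol's analyses.

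**The concern.** A missing EOS visit does not mean that there are no post-dose safety data. A participant who dies soon after the last dose, or who is followed only by telephone, can have AEs and SAEs on file with onset after that dose. As the SAP is written, those events fall outside the on-treatment period and so outside the treatment-emergent AE and SAE tables. Whether an event is counted then depends on whether a later visit took place, not on how soon after dosing the event began.

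The omission need not be random. Protocol 9.1.1 requires treatment to stop for, among other things, PAH deterioration needing hospitalization and severe drug-related AEs. Participants who stop for such reasons may be less able to attend EOS. The documents give no data on this, so it is a possibility and not a finding.

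**Working it through.** **Reproducing the plan's post-dose window.** The assessment schedule (Protocol Table 8-1) puts the end-of-treatment visit at Day 169 (+5) and EOS at Day 199 (±5).

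- Nominal gap: 199 − 169 = 30 days, which matches the stated figure of about 30 days.
- Range over the visit windows: 194 − 174 = 20 days to 204 − 169 = 35 days.

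**Which definition governs the AE tables.**

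1. SAP 2.7 restricts safety tables and figures to on-treatment data.
2. SAP 2.7.1 takes the period for the AE tables from SAP 2.1.1.
3. SAP 2.1.1 ends the period at the last dose when there is no EOS visit, whatever the reason.
4. Protocol 12.5.2 requires the start date of a tabulated event to lie in the period.

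An event that starts after the last dose in a participant without EOS is therefore not counted.

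**Are such events collected?** Yes. AEs are monitored for at least 30 days after the last dose, SAEs are reported until 30 days after it, and both are sought by telephone or email when visits are missed.

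**Worked case.** Take a last dose on Day 85, an AE starting on Day 95, no EOS visit and no rollover.

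- SAP 2.1.1: the period ends on Day 85. Since 95 > 85, the AE is not counted.
- Last dose plus 30 days: the period ends on Day 115. Since 95 ≤ 115, the AE is counted.
- The same participant with an EOS visit about 30 days after the last dose: counted.

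Likewise, an SAE starting 5 days after the last dose in someone who dies on day 10 is missing from the SAE table, although the death appears in the death summary.

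**Share of the window lost**, as 30 / (last dose day + 30):

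| Last dose | Period ends under SAP 2.1.1, no EOS | Last dose + 30 days | Share lost |
|---|---|---|---|
| Day 29 | Day 29 | Day 59 | 30/59 = 51% |
| Day 85 | Day 85 | Day 115 | 30/115 = 26% |
| Day 169 | Day 169 | Day 199 | 30/199 = 15% |

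**Effect on a table row.** Randomizing 44 participants 3:1 gives 44 × 3/4 = 33 on LTP001 and 44 × 1/4 = 11 on placebo. One participant left out changes an incidence by at most 1/33 = 3.0 percentage points (LTP001) or 1/11 = 9.1 points (placebo), and by nothing if already counted in that row.

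**Number affected.** The documents do not give it. If it is assumed to be no larger than the planned dropout (44 − 40 = 4, about 10%), the range is 0 to 4 participants.

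**The case against.** The strongest reply is that the clause was meant for extension rollovers, that SAP 2.7 restates the period without it, and that SAP 2.7.1 defines treatment-emergent events as those starting after first dose, which the day-5 SAE satisfies. The intention is plausible, but the wording is not limited to rollovers and a programmer will derive the date from the wording. SAP 2.7 gives no end date when EOS is missing, so it cannot settle the case, and SAP 2.7.1 names 2.1.1. The treatment-emergent wording sets only a start. What stands is that the SAP contains two definitions, so the loss follows from the one the AE section cites and is not beyond dispute.

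The second reply is that few people are affected. This largely stands. Week 29 may be done off-site, participants who stop treatment are expected at follow-up, those leaving the study are offered a final evaluation, and those lost or withdrawn from contact supply little to exclude. The documents do not say whether a Week 29 telephone call counts as an EOS visit. If it does, the group shrinks further. Early post-dose deaths and some participants who refuse visits remain. The 3.0 and 9.1 points are ceilings for one participant, based on planned randomized numbers; they do not estimate the effect.

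Third, little depends on these tables. SAP 2.7.2 keeps the deaths ("The number and percentage of deaths, including on-treatment and post-treatment deaths, will be summarized by treatment group"), AE listings are not restricted to the period, SAE reporting is unchanged, and the primary endpoint is not involved. All of this is correct.

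Fourth, the mismatch with SAP section 4 is a weak point. The SAP was written against protocol version 02 and the protocol supplied is version 03. Protocol 12.5.2 is also silent on a missing EOS visit, so the fallback can be read as filling a gap. The conclusion does not need this point.

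**Conclusion.** The concern holds. As written, participants who do not roll over and have no EOS visit get a post-dose window of 0 days instead of about 30 in the AE and SAE tables, although the protocol collects their events over that time. This rests on reading SAP 2.1.1 literally and on following the cross-reference in SAP 2.7.1.

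The effect is on tabulation only and probably concerns few people. It should still be corrected, because safety tables ought to treat participants alike and the data needed are already planned.

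**What to change.** Use one definition in SAP 2.1.1 and 2.7: the on-treatment period runs from first dose to the EOS visit, or to last dose + 30 days if there is no EOS visit, and for rollovers is cut at the day before the first extension dose. For a rollover who goes straight into the extension, that cut falls at the last dose in this study, so the purpose of the present clause is kept. How the transition works is left to the extension protocol, so the cut date should be checked against it.

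Two smaller points belong in the same edit. Replace the undefined term for the last randomized dose with the date of last administration that SAP 2.1.1 already defines. State whether a Week 29 telephone contact counts as an EOS visit.

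Align Protocol 12.5.2, or list the difference in SAP section 4.

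The cost is one sentence in each of SAP 2.1.1 and 2.7 and one date derivation in the programs. No new data are needed.
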